### **Study Timelines**

Duration of clinical phase: 12 weeks corresponding to 28 days of investigational product (IP) + 8 weeks of follow-up without IP.

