#### **10.2.6 Adverse event collection**

Adverse events will be collected throughout the study and at every visit after consent. The medically-qualified investigator will be available to provide clinical judgment on all trial-related medical issues including adverse events and clinical laboratory values.

As a precautionary measure, specific attention will be paid to any potential serotonergic syndrome, particularly the following symptoms agitation, mental status changes (confusion, hypomania), myoclonus, shivering, tremor, hyperreflexia, ataxia, severe diarrhea or high fever will be checked carefully.

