#### **11.1.6 Visit 6 End Study visit (Day 84±3)**

The following tests and procedures will be performed at Visit 6 and in the case of premature withdrawal during the study (i.e. prior to Visit 6):

- Inquiring about adverse event and fill an adverse event form if any
- Checking for concomitant medication
- Physical examination including weight and evaluation of main body systems/regions,
- Vital signs: supine blood pressure and heart rate, temperature
- Otologic examination and tympanometry
- Audiometric tests: Pure tone audiometry and OAE tests (optional)
- Word and Speech recognition Tests
- Pregnancy test (for WOCBP)

The patient will be asked to complete specific questionnaires:

- Tinnitus and Vertigo Severity (NRS)
- QoL: EQ-5D-5L
- TFI

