#### **13.5.4.1 Adverse events**

Each adverse event will be coded to a “Preferred Term” and associated “System-Organ Class” according to an established and validated adverse reaction dictionary (MedDRA) before the randomised treatment code is broken. The adverse event endpoints are number of subjects experiencing:

- at least one event,
- an event under each recorded Preferred Term,
- an event under each recorded System-Organ Class.

These endpoints apply to all adverse events, regardless of relationship of the event to the study drug.

All safety analyses will be performed on the safety analysis set using descriptive statistics.

Adverse events (AEs) will be evaluated for severity and coded using MedDRA. They will be summarized by system organ class and preferred term. Separate summaries of treatment-emergent AEs (TEAEs) will be generated for the following:

- All TEAEs
- Severe TEAEs
- Serious TEAEs
- TEAEs leading to treatment discontinuation
- TEAEs resulting in death

Treatment-emergent adverse events (TEAE) are defined as events occurring after the first dose intake of randomised study drug, and up to and including five half-lives after the last dose of study drug. Additionally, events present before the first dose of randomised study drug, but worsening under treatment are considered as TEAE. Events with treatment status unclear because the onset date and/or the dates of first/last study drug intake are missing or incomplete will be considered as TEAEs.

An AE that will not qualify as a TEAE will be considered as a Non-TEAE.

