#### 6.14.1 Adverse Events

	Sponsor:	Sensorion
	Protocol Number:	SENS 401-201
STATISTICAL ANALYSIS PLAN. PHASE 2-3-4		

A treatment emergent adverse event (TEAE) is defined as any AE that has an onset on or after the first dose of study drug (without limitation after end of treatment).

Events with treatment status unclear because the onset date and/or the dates of first/last study drug intake are missing or incomplete will be considered as TEAEs.

Late AE is defined as any AE that has an onset on or later than 3 days after the last study treatment intake.

A treatment-related AE is defined as an AE as being possibly or probably related to the study drug. If an AE has missing or not assessable relationship it is assumed to be related to the study drug for analysis purposes.

Maximum severity will be assumed for an AE with missing severity.

All AEs will be coded using the most recent MedDRA version available at time of database lock. Summaries over system organ class (SOC) and preferred term (PT) by treatment groups, and listings of all TEAEs, Serious Adverse Events (SAEs), AEs leading to withdrawal, and AEs leading to death will be presented. The following tables will be presented for AEs:

- Overall incidence and the number of TEAEs, treatment-related TEAEs, SAEs, TEAEs leading to withdrawal, and TEAEs leading to death.
- TEAE by system organ class and preferred term, incidence and number of events
- Treatment-related TEAE by system organ class and preferred term, incidence and number of events
- Serious TEAE by system organ class and preferred term, incidence and number of events
- Severe TEAE by system organ class and preferred term, incidence and number of events
- TEAE by system organ class, preferred term and maximum severity, incidence
- Treatment-related TEAE by system organ class, preferred term and maximum severity, incidence
- TEAE leading to early withdrawal by system organ class and preferred term, incidence and number of events
- Listing of serious AEs (presented in the Table section of the appendices).
- Listing of AEs leading to withdrawal (presented in the Table section of the appendices)
- Listing of AEs leading to deaths (presented in the Table section of the appendices).

	Sponsor:	Sensorion
	Protocol Number:	SENS 401-201
STATISTICAL ANALYSIS PLAN. PHASE 2-3-4		

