In counting the number of AEs reported, a continuous event (i.e. reported more than once and which did not cease), will be counted only once; non-continuous AE reported several times by the same subject will be counted as multiple events.

A late TEAE is defined as a TEAE that has an onset date 3 days or more after the last intake of study drug.

The outputs listed above will be repeated on the late TEAEs only.

All AEs will be listed (with flags identifying TEAEs and late TEAEs).

SAEs not classified as treatment-emergent will be displayed in a separate listing.

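### The SAP's open-ended TEAE window leaves no planned table of on-treatment subject incidence or maximum severity

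*SAP*

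**What the plan says.** **Protocol.** Section 13.5.4.1 counts as treatment-emergent those events that start after the first dose, "up to and including five half-lives after the last dose of study drug". Its TEAE summaries (all, severe, serious, leading to discontinuation, fatal) use that window.

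**SAP.** Section 6.14.1 removes the end of the window: onset on or after the first dose, "without limitation after end of treatment". It then adds one subset: "A late TEAE is defined as a TEAE that has an onset date 3 days or more after the last intake of study drug". On outputs it says: "The outputs listed above will be repeated on the late TEAEs only". Section 8, item 9, declares the change of definition but gives no reason. In the output list of section 10, each all-TEAE table (14.3.1.1.1 to 14.3.1.8.1) is paired with a late table (14.3.1.1.2 to 14.3.1.8.2). No table is restricted to the treatment period.

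**Length of the window.** Under Study Timelines the protocol summary gives "12 weeks corresponding to 28 days of investigational product (IP) + 8 weeks of follow-up without IP". Collection is not cut off at the end of treatment. Section 10.2.6 says "Adverse events will be collected throughout the study and at every visit after consent", and the Day 84 visit in section 11.1.6 includes "Inquiring about adverse event and fill an adverse event form if any".

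**Metrics.** Six of the eight TEAE table types report both subjects and events, for example "TEAE by system organ class and preferred term, incidence and number of events". The two maximum-severity tables report subject incidence only. SAP 6.14.1 also plans a listing of all adverse events, with flags for TEAEs and late TEAEs.

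**The concern.** The comparison that speaks most directly to tolerability is the percentage of subjects in each arm with an event while exposed. The protocol's definition would have delivered it, give or take a short tail. The SAP replaces that display instead of adding to it. The main tables mix four weeks of exposure with eight drug-free weeks, and the companion tables show only the drug-free part.

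One of the study's secondary objectives is to confirm safety at the studied dosage regimen. Protocol 5.4.1 names constipation and abdominal pain as the main adverse events of the class, usually mild or moderate. Effects of this kind would be expected during exposure. In arms of 37 they are easily blurred when background events from another 56 days are added to every arm.

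The SAP isolates the treatment period elsewhere: a table of concomitant medication taken while on study drug (14.3.8.3), and post-baseline suicidality outcomes defined during double-blind treatment (6.2.12). Adverse events have no equivalent.

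**Working it through.** **1. Share of the window off drug** (Protocol, Study Timelines).
- The plan's figure reproduces: 28 + 8 × 7 = 84 days = 12 weeks.
- Off-drug share = 56/84 = 66.7%. With the last visit at Day 81 or Day 87 it is 53/81 = 65.4% or 59/87 = 67.8%.

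**2. What subtraction can and cannot give** (SAP 6.14.1).
- Events: each event has one onset and is either late or not. On-treatment events = TEAE events − late events, exactly, wherever events are counted.
- Subjects: a subject with an on-treatment event and a late event appears in both tables. If T subjects have a TEAE and L have a late TEAE, the number with an on-treatment event lies anywhere from T − L to T. For an illustrative T = 15 and L = 9, that is 6 to 15.
- Maximum severity: these tables give incidence only, so the same limit applies and there is no event count to fall back on.

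**3. Size of the dilution** (assumed rates; the documents give none). Let p be the 28-day on-drug risk and q the 56-day off-drug risk, the same in both arms. Then

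84-day risk = 1 − (1 − p)(1 − q), so 84-day difference = (1 − q) × on-drug difference.

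If the off-drug background continues at the placebo arm's on-treatment rate, 1 − q = (1 − p_placebo)².

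| Assumed on-drug risks | 1 − q | 84-day risks | Difference (points) | Risk ratio |
|---|---|---|---|---|
| 10% v 5% | 0.9025 | 18.8% v 14.3% | 5.0 → 4.5 | 2.0 → 1.32 |
| 20% v 10% | 0.81 | 35.2% v 27.1% | 10.0 → 8.1 | 2.0 → 1.30 |
| 40% v 20% | 0.64 | 61.6% v 48.8% | 20.0 → 12.8 | 2.0 → 1.26 |
| 10% v 2% | 0.9604 | 13.6% v 5.9% | 8.0 → 7.7 | 5.0 → 2.3 |

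For the second row: 1 − 0.8 × 0.81 = 0.352 and 1 − 0.9 × 0.81 = 0.271.

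If the off-drug background is lower, the shrinkage is smaller. Take 20% v 10% on drug with 5% per 28 days off drug: 1 − q = 0.95² = 0.9025, giving 27.8% v 18.8%, a difference of 9.0 points and a ratio of 1.48.

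For event counts, an on-drug rate ratio of 2.0 becomes (28 × 2 + 56)/84 = 1.33 over 84 days. The expected absolute difference in counts does not change.

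**4. Would a cut at 3 days approximate the protocol's window?** The documents do not state the half-life. Protocol 5.4.2 gives Cmin 43.3 and Cmax 120 ng/mL at 43.5 mg BID. Assuming mono-exponential decline over the 12-hour interval and a peak at 0 to 3 hours:
- half-life = (12 − tmax)/log2(120/43.3) = 12/1.47 to 9/1.47 = 8.2 to 6.1 h;
- five half-lives = 41 to 31 h, or about 1.7 to 1.3 days.

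On that assumption, TEAEs not flagged late cover the protocol's window and run slightly past it.

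**The case against.** The strongest case on the other side is that this is a disclosed choice with real merit. An open-ended definition misses no delayed event, and the SAP adds a full parallel late set. Treatment-related and withdrawal tables also address tolerability, and the flagged listing lets anyone rebuild on-treatment incidence. All of that stands. It makes the request an addition and not a correction of an error. It does not supply the missing tabulation: hand-counting from a listing is not a planned analysis.

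The size of the dilution is also open to challenge. The rates are assumed, and a constant background may be too high after Day 28. During treatment patients also take oral corticosteroids and are asked about events at Days 7, 14 and 28; afterwards there is one scheduled visit, at Day 84. Events may therefore cluster in the treatment period and be diluted less. This stands too, so the table above is an illustration and not an estimate.

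A reader might infer three stronger things that the documents do not support:
- **That on-drug differences are lost.** Event counts follow by subtraction, and the listing carries the flags.
- **That the Part 2 dose would be chosen on diluted tables.** SAP section 1 limits this document to the clinical study reports and places the DMC analyses in a separate plan, which is not available here. Protocol 7.3 sets dose selection at the point when Part 1 patients have completed four weeks of treatment, not at Day 84.
- **That a test loses power or significance.** Protocol 13.5.4 makes safety descriptive, with no hypothesis testing.

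**Conclusion.** The point holds as a gap in the planned CSR tables. About two-thirds of the main TEAE window is off drug. On-treatment subject incidence and maximum severity appear in no planned table and cannot be derived from the tables that are planned. The window length and the limits of subtraction follow directly from the documents.

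The direction of the bias, towards smaller differences and ratios in subject percentages, rests on off-drug background being similar across arms. Its size rests on assumed rates. Where the on-drug ratio is 2.0, the 84-day ratio is about 1.3 under a constant background and about 1.5 in the lower-background example. For rare events the absolute difference barely moves, although the ratio still shrinks. The match between the 3-day cut and five half-lives is likewise an inference from Cmin and Cmax until the half-life is stated.

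This is a worthwhile, low-cost improvement to a descriptive analysis. It is not an undeclared departure from the protocol, since section 8 of the SAP records the change.

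**What to change.** - Keep the all-TEAE and late-TEAE tables as planned.
- Add a third set: tables 14.3.1.1.1 to 14.3.1.8.1 repeated on TEAEs not flagged late (onset less than 3 days after the last intake), for Part 1 (a) and Part 2 (b). That is 8 × 2 = 16 tables. Name this set in 6.14.1 as the on-treatment description in the CSR.
- State the half-life in 6.14.1 so that the 3-day cut can be related to the protocol's five half-lives, and say whether the two windows are meant to agree.
- Give the reason for the changed definition in section 8, item 9.

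The flag and the table shells already exist, so the programming is a re-run on the complement of the late subset. Nothing is removed. The cost is a longer table set to produce and review.

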### 6.14.2 Laboratory Data

Descriptive statistics of the observed values and change from baseline (continuous data) will be presented by treatment group and visit for each hematology, serum chemistry, and C-reactive protein parameter. For categorical laboratory parameters, subject counts within each category will be summarized. Shift tables from baseline to each post-baseline visit will also be presented, as applicable.

Each measurement (continuous data) will be classified as below, within, or above normal range, based on ranges supplied by the laboratory used. This study utilizes local laboratories only and therefore each local laboratory will provide its reference ranges. Shift tables in relation to the normal range from baseline to each follow-up visit will be presented.

Moreover, the number and percentage of subjects with treatment-emergent marked laboratory abnormalities will be tabulated for each laboratory parameter for which marked abnormalities are defined in the table below. For a given parameter, percentages will be based on the number of subjects at risk: those not meeting the criterion at baseline (or having a missing baseline value) and having at least one post-baseline value (including post-baseline value after last intake of study drug). The marked laboratory date abnormalities are defined as follows:

		Sponsor:	Sensorion
		Protocol Number:	SENS 401-201
STATISTICAL ANALYSIS PLAN. PHASE 2-3-4			

Category	Lab Test/ Examination Name	Unit	Marked Abnormalities				
			LL	LLL	HH	HHH	HHHH
CHEMISTRY	Alanine Aminotransferase	U/L			>3ULN	>5ULN	>8ULN
CHEMISTRY	Albumin	g/L	<30	<20			
CHEMISTRY	Alkaline Phosphatase	U/L			>2.5ULN	>5ULN	
CHEMISTRY	Aspartate Aminotransferase	U/L			>3ULN	>5ULN	>8ULN
CHEMISTRY	Bilirubin	umol/L			>2ULN	>5ULN	
CHEMISTRY	Calcium	mmol/L	<2.0	<1.75	>2.9	>3.1	
CHEMISTRY	Creatine Kinase	U/L			>5ULN	>10ULN	
CHEMISTRY	Creatinine	mmol/L			>1.5ULN or (>1.5baseline if baseline > ULN)	>3ULN or (>3baseline if baseline>ULN)	
CHEMISTRY	Creatinine Clearance	mL/min/ 1.73m 	<60	<30			
CHEMISTRY	Gamma Glutamyl Transferase	U/L			>2.5ULN	>5ULN	
CHEMISTRY	Glucose	mmol/L	<3.0	<2.2	>8.9	>13.9	
CHEMISTRY	Phosphate	mmol/L	<0.8	<0.6			
CHEMISTRY	Potassium	mmol/L	<3.2	<3.0	>5.5	>6.0	
CHEMISTRY	Sodium	mmol/L	<130		>150	>155	
CHEMISTRY	Triglycerides	mmol/L					
CHEMISTRY	Urate	umol/L			>590	>720	
CHEMISTRY	Urea	mmol/L			>2.5ULN	>5ULN	
HEMATOLOGY	Eosinophils	10  /L			>5.0		
HEMATOLOGY	Hematocrit	Ratio	<0.32(men), <0.28(women)	<0.20	>0.60(men), >0.55 (women)	>0.65	
HEMATOLOGY	Hemoglobin	g/L	<100	<80	>ULN+20 (or >baseline+20 if baseline>ULN)	>ULN+40 (or >baseline+40 if baseline>ULN)	
HEMATOLOGY	Leukocytes	10  /L	<3.0	<2.0	>20	>100	
HEMATOLOGY	Lymphocytes	10  /L	<0.8	<0.5	>4.0	>20	
HEMATOLOGY	Neutrophils	10  /L	<1.5	<1.0			
HEMATOLOGY	Platelets	10  /L	<75	<50	>600	>999	

A listing of any clinically significant laboratory measurements recorded throughout the study will be presented. For lab parameters that have defined marked abnormalities, the most extreme

	Sponsor:	Sensorion
	Protocol Number:	SENS 401-201
STATISTICAL ANALYSIS PLAN. PHASE 2-3-4		

abnormality will be listed. All laboratory assessments, including urine and serum pregnancy tests, will also be listed.

### 6.14.3 Vital Signs

Descriptive statistics for observed values and changes from baseline in the following vital signs will be presented by treatment group and visit:

- Systolic blood pressure (mmHg)
- Diastolic blood pressure (mmHg)
- Heart rate (bpm)
- Body temperature (degrees Celsius)
- Body weight (kg)

Moreover, the number and percentage of subjects with treatment-emergent marked abnormality will be tabulated for each parameter. Percentages will be based on the number of subjects at risk for the parameter: those having a baseline value and at least one post-baseline value (including post-baseline value after last intake of study drug). The marked vital sign abnormalities are defined as follows:

Parameter	Abnormality
SBP (mmHg)	≤ 95 mmHg and decrease from baseline ≥ 20 mmHg, ≥ 160 mmHg and increase from baseline ≥ 20 mmHg
DBP (mmHg)	≤ 45 mmHg and decrease from baseline ≥ 10 mmHg, ≥ 110 mmHg and increase from baseline ≥ 10 mmHg
HR (bpm)	≤ 50 bpm and decrease from baseline ≥ 20 bpm, ≥ 120 bpm and increase from baseline ≥ 20 bpm

### 6.14.4 Physical Examination

The body systems within the physical examination data will be summarized by treatment and visit. In addition, shift tables in terms of findings (Normal, Abnormal NCS, Abnormal CS) from baseline to Day 28 (EoT) and Day 84 (EoS/Follow-up) for each body system will be presented. Details of clinically significant findings will be listed.

### 6.14.5 Otoscopy

Otoscopy is to be done just before each hearing assessment at every visit to rule out possible outer-ear abnormality, such as otitis media, tympanic perforation. It is part of the standard of care. Findings (Normal, Abnormal NCS and Abnormal CS) will be summarized for each ear by

	Sponsor:	Sensorion
	Protocol Number:	SENS 401-201
STATISTICAL ANALYSIS PLAN. PHASE 2-3-4		

treatment group and visit. In addition, shift tables from baseline to all post-baseline visits will be presented for each ear by treatment group.

All otoscopy data will be listed.

### **6.14.6 Tympanometry**

Tympanometry will follow the otoscopy in order to test the condition of the middle ear and mobility of the eardrum (tympanic membrane) and the conduction bones by creating variations of air pressure in the ear canal.

Findings (Normal, Abnormal NCS, Abnormal CS) will be summarized for each ear by treatment group and visit. Shift tables from baseline to each post-baseline visit will be presented for each ear by treatment group.

All tympanometry data will be listed.

### **6.14.7 Columbia-Suicide Severity Rating Scale (C-SSRS)**

C-SSRS will be used to assess suicidal ideations and behaviors. Number of subjects that responded ‘yes’ to any of the C-SSRS Suicidal Ideation Items, as described in Section 6.2.12, will be presented by treatment group, and will be tabulated separately for baseline and post-baseline assessments. Similarly, number of subjects that responded ‘yes’ to any of the C-SSRS Suicidal Behavioral Items, as described in Section 6.2.12, will be presented by treatment group, and will be tabulated separately at baseline and post-baseline assessments.

Derived C-SSRS data as described in Section 6.2.12 will be listed for baseline and post-baseline assessments for all subjects.

## **7 INTERIM ANALYSIS**

Protocol version 4.0 introduced two interim GST looks to be performed during Part 1 of the study, which may lead to early discontinuation of Part 1 for futility or efficacy.

The GST design was defined with a 75% power for a standardized difference of means of 0.546 (15/26.79), an overall 5% one-sided significance level (with a gamma function of parameter -2 as Hwang-Shih-DeCani alpha spending function) and a binding futility procedure (with a gamma function of parameter -4 as Hwang-Shih-DeCani beta spending function). At each GST look, the z-score statistic was to be calculated for the estimated difference of high dose versus placebo. The GST looks were planned for 41 (first GST look), 55 (second GST look) and 74 (final analysis of

		Sponsor:	Sensorion
		Protocol Number:	SENS 401-201
STATISTICAL ANALYSIS PLAN. PHASE 2-3-4			

Part 1) patients available for the high dose and the placebo together. The GST design can be summarized as follows:

Analysis stage	Futility		Efficacy	
	nominal p-value limit	z-score limit	nominal p-value limit	z-score limit
Anticipated cumulative number of subjects in high dose + placebo				
N = 41	$\geq 0.6345$	$\leq 0.344$	$\leq 0.075$	$\geq 2.432$
N = 55	$\geq 0.8047$	$\leq 0.859$	$\leq 0.150$	$\geq 2.170$
N = 74	$\geq 0.9500$	$\leq 1.645$	$\leq 0.0500$	$\geq 1.645$

In this GST design, the first interim look, second interim look and final analysis were planned when 63, 85 and 111 patients, respectively (when 41, 55, 74 patients could be expected in the high dose and placebo groups) have been randomized up to the date still theoretically compatible with reaching Day 28 and having the data centrally reviewed before he considered GST look. However, irrespective of the actual number of patients in high dose and placebo observed in the GST look, the z-score limits for futility and efficacy were to be used without any change.

Further details of the GST analyses are described in a separate SAP. The GST analyses were to be undertaken by a separate statistical group contracted by the sponsor.

The first GST look was performed, and the outcome was a recommendation to continue Part 1 in the absence of crossing of any boundary. The second GST look was not performed because all amendment protocol approvals were not obtained yet at time when the sample size of the second GST was reached. The final look will finally not be performed as it does not have enough added value compared to the analysis planned in the DMC SAP section 2.6 (same boundary p-value of 0.0500 one-sided for both analyses).

